4) Patients with poor bowel preparation, i.e., patients with a total score of <6 or any bowel segment of <2 on the Boston Bowel Preparedness Scale score for poor bowel preparation).
(4) Research methods and contents:

1) Preparation for colonoscopy: Routine ECG, infectious disease screening were performed before examination. Patients were advised liquid diet 1 day before and fasted from food and water on the day of examination according to the "Chinese Guidelines for Gastrointestinal Tract Preparation for Endoscopy (2019, Shanghai)". Patients were advised to take oral polyethylene glycol electrolyte powder or sodium phosphate solution for bowel preparation. The last bowel movement should be clear liquid stool before examination.

2) Colonoscopy: All patients took left lateral position with flexed knees close to abdomen. Olympus CF-H290 high definition electronic colonoscope was used under general anesthesia. The endoscopist advanced the colonoscope to the cecum and started withdrawal observation of the colon and rectum mucosa. Polyp lesions found were photographed, removed with biopsy forceps and sent for pathology. When the colonoscope was withdrawn to the rectum after the first examination, patients were randomly allocated to the standard group or second insertion group. Computer-generated randomization numbers divided patients into two groups with allocation information sealed in numbered, opaque envelopes. The endoscopist was blinded to group assignments until completion of first examination of the proximal rectum when the envelope was opened. For the second insertion group, the sigmoid colon was re-inserted with deliberate folds advancement to unfold the folds, and further observations were made during both insertion and withdrawal, polyp lesions found were photographed, removed and sent for pathology. Withdrawal to the anus was then performed in standard manner. The standard group had standard withdrawal observation from rectum to anus for polyp detection and removal.

3) Collection of patient data:

General information: height, weight, gender, age, smoking, drinking, abdominal circumference, hypertension, diabetes, family history of colorectal cancer etc.

Special data: number, location, morphology (pedunculated, sessile), size (<5mm,

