5-10mm, >10mm) of polyps, pathology of polyps (inflammatory, hyperplastic, adenomatous); BBPS score for bowel cleanliness; time of first withdrawal, second sigmoid insertion, withdrawal (excluding time for polyp biopsy or treatment); vital signs like blood pressure, heart rate, oxygen saturation (recorded every 5 minutes) of patients during colonoscopy; adverse reactions after procedure (abdominal pain, bloating, nausea, vomiting).

4) Calculation and analysis of data:

(1) Separately calculate and compare the ADR of sigmoid colon between standard and second insertion groups: ADR= number of patients with detected sigmoid adenoma / total number of patients in each group.

(2) Separately calculate and compare the PDR of sigmoid colon between standard and second insertion groups: PDR= number of patients with detected sigmoid polyps / total number of patients in each group

(3) Calculate and compare the postoperative adverse reaction rate between two groups: Adverse reaction rate= number of patients with adverse reactions / total number of patients in each group. 5) Statistical methods: Analysis was performed using SPSS 26.0 software. Counting data were expressed as cases (n) and percentage (%), inter-group comparison was performed using χ^2 test, χ^2 correction or Fisher's exact test. Measurement data were expressed as Mean ± SD, inter-group comparison was performed using t test, t' test or non-parametric test (U test). P <0.05 was considered statistically significant.

5. Expected research outcomes

(1) Analyze the impact of a second sigmoid colon insertion on the adenoma detection rate (ADR) and related risk factors for missed adenomas, thereby improving clinicians' understanding of the second insertion method;

(2) Publish 1 sci paper.

6. Other ethical issues

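### Sigmoid ADR is to be compared by an unadjusted test only: a valid analysis, but precision available from baseline values, and above all from the first-pass sigmoid finding, goes unused

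*Combined protocol and SAP*

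**What the plan says.** All references are to the combined protocol and SAP, section 4 (Research Content) unless stated.

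- **Endpoint.** Calculation and analysis of data, item (1), says "Separately calculate and compare the ADR of sigmoid colon between standard and second insertion groups" and defines sigmoid ADR per patient as "number of patients with detected sigmoid adenoma / total number of patients in each group". No endpoint is labelled primary, but sigmoid ADR is listed first and matches the first objective in section 3.
- **Test.** For counts, Statistical methods says "inter-group comparison was performed using χ^2 test, χ^2 correction or Fisher's exact test", with "P <0.05 was considered statistically significant". Sidedness is not stated. No adjusted model, covariate list or confidence interval appears.
- **Covariates.** Collection of patient data lists "height, weight, gender, age, smoking, drinking, abdominal circumference, hypertension, diabetes, family history of colorectal cancer etc". It also lists polyp number, location and pathology, but does not say that the examination pass in which a polyp was found is recorded.
- **Allocation.** The Colonoscopy item describes computer-generated numbers in sealed envelopes, opened once the first withdrawal has reached the rectum. Stratification is not mentioned. After allocation the standard group is examined only from rectum to anus.
- **Risk factors.** Section 5 expects to "Analyze the impact of a second sigmoid colon insertion on the adenoma detection rate (ADR) and related risk factors for missed adenomas". No method is given, and the aim is not linked to the comparison between arms.

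**The concern.** In a randomised comparison of a binary outcome, adjusting for prespecified prognostic baseline values and standardising over all randomised patients estimates the same quantity, the difference in ADR. It usually does so with a somewhat smaller standard error, and it removes the part of the estimate that comes from chance differences between arms in those values. Here several candidate covariates will be in the dataset anyway, and neither the allocation nor the analysis uses them.

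Two features add weight. Recruitment is a three-month window at one centre with no stated sample size, so unless the window is extended, lost precision cannot be recovered by enrolling more patients. And with many covariates collected and no list fixed, any adjusted result reported later would be open to the objection that its covariates were chosen after the data were seen.

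**Working it through.** The plan gives no sample size, power, expected ADR or effect size, so there is no figure to reproduce. The rates, arm sizes and covariate strengths below are assumptions; a two-sided 5% level and 1:1 allocation are assumed too.

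**1. Crude precision, 15% v 20%, 300 per arm.**
SE = √[(0.15×0.85 + 0.20×0.80)/300] = √(0.2875/300) = 3.1 percentage points, a 95% half-width of about 6.1 points. With the pooled null SE √(2×0.175×0.825/300) = 3.10 points, power = Φ[(5 − 1.96×3.10)/3.10] ≈ 36%.

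**2. Patient-level covariates only.**
Simulations compared the crude difference with the logistic-standardised difference. The odds ratios were weak (1.2 per SD of age, 1.3 for gender, 1.2 for smoking), typical (1.5, 1.7, 1.5) or strong (2.0, 2.2, 2.0). At 300 per arm:

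| Covariates | Variance reduction | Shift in estimate exceeded in 1 trial in 20 |
|---|---|---|
| weak | about 1% or less | 0.8 to 0.9 points |
| typical | 3% to 4% | 1.4 points |
| strong | 10% | 2.0 to 2.1 points |

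The ranges span two separate simulations. Simulated power levels are noisy, so power is better obtained from the effective sample size n/(1 − R²), where R² is the variance reduction:
- R² = 1%: 303 per arm, power 36.7%
- R² = 3%: 309 per arm, power 37.3%
- R² = 10%: 333 per arm, power 39.7%

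Against 36.4% unadjusted, the gain is about 0 to 3 points.

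With weak covariates the adjusted/crude variance ratio was 1.00 at 200 per arm and 1.03 at 100 per arm. With typical covariates it was 0.98 and 1.00. So in small arms the gain can vanish or become a trivial loss.

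**3. At a size giving 80% crude power.**
15% v 20% needs 906 per arm. Multiplying by (1 − R²) gives 888 (R² 2%), 861 (5%) or 816 (10%). Keeping 906 per arm, power becomes 80.8%, 82.0% or 84.0%.

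**4. Chance imbalance.**
An imbalance of 1.96 SE in a prognostic score at 300 per arm is 1.96×√(2/300) = 0.16 SD. The shift in the ADR difference is about 0.16×b×0.15×0.85: 1.0 point for b = 0.5 and 1.8 points for b = 0.9 (log odds ratio per SD). Both are well inside the crude half-width of 6.1 points.

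**5. First-pass sigmoid adenoma status.**
The first-pass specimen is taken before allocation, even though pathology is read later. Since the standard group has no further sigmoid examination, its outcome should equal its first-pass result. Let p₁ be the first-pass ADR and q = (p₂ − p₁)/(1 − p₁) the chance that a first-pass-negative patient has an adenoma found on the second look. Per-arm variance terms (multiply by 1/n):
- crude: p₁(1 − p₁) + p₂(1 − p₂)
- adjusted: (1 − p₁)q(1 − q) + q²p₁(1 − p₁)/2

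For 15% v 20%, q = 0.05/0.85 = 0.0588. Crude = 0.2875; adjusted = 0.0471 + 0.0002 = 0.0473; ratio 0.164. At 300 per arm the SE falls from 3.1 to 1.3 points. Other pairs:

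| p₁ v p₂ | Adjusted/crude variance |
|---|---|
| 10% v 15% | 0.218 |
| 15% v 22% | 0.216 |
| 20% v 25% | 0.136 |
| 20% v 30% | 0.240 |

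Under this assumption every first-pass-positive patient has the outcome and no first-pass-negative control does. A logistic model with arm and first-pass status will then separate, so a stratified or linear-model risk difference is needed.

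**The case against.** The strongest reply is that nothing is wrong. A crude comparison of two proportions is valid after randomisation and matches the stated endpoint, and its type I error and confidence interval already allow for chance imbalance. That stands. In null simulations at 906 per arm the crude type I error was 5.1% and 6.1% and the adjusted 4.9% and 5.5%, all near 5% given a simulation error of about 0.6 points.

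A reader might go further and infer that the planned ADR comparison is biased, or that an older or more male arm could not be told apart from a real effect. The documents do not support this: allocation is random, and such imbalance is random error.

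It is also fair that the gain from patient-level covariates is small and rests wholly on assumed inputs, and that a model with those covariates alone would forgo most of the available precision. That is a reason to add first-pass status, not to leave the plan as it is.

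Two narrower points also stand. The documents do not say when the covariates are recorded. Age and BMI are entry criteria, so they are known before allocation; for gender, smoking and family history this is inferred from their being pre-existing traits. And the risk-factor aim concerns missed adenomas, a separate question, so it does not itself call for an adjusted comparison between arms.

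**Conclusion.** The point holds as a missed efficiency gain. The plan names only unadjusted tests for sigmoid ADR, collects usable covariates, and describes neither stratified allocation nor an adjusted analysis. From patient-level covariates alone the benefit is modest: about 0% to 10% of the variance and 0 to 3 points of power at an assumed 15% v 20% and 300 per arm, with none if the covariates are weak and the arms small. The larger gain, a variance of about 14% to 24% of crude, depends on first-pass sigmoid status being recorded by pass and on the control outcome being fixed by that pass. The Colonoscopy item makes the second condition likely; the data list does not guarantee the first. None of these sizes can be derived from the documents alone.

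**What to change.** Before data are seen, amend section 4 as follows.

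1. **Main sigmoid ADR comparison (Calculation and analysis of data; Statistical methods).** State it as a risk difference with 95% CI, standardised over all randomised patients, from a logistic model with arm, age, gender, BMI, smoking and family history of colorectal cancer. Use a robust or bootstrap standard error and simple imputation of missing covariate values.
2. **Data collection.** Record for each sigmoid lesion whether it was found before or after the envelope was opened, and label specimens accordingly.
3. **First-pass status.** Include first-pass sigmoid adenoma status as a baseline covariate. Name in advance the standardised linear model or stratified risk difference to be used if the logistic fit separates.
4. **Supportive results.** Keep the ADR formula, the crude rates and the chi-square test.
5. **PDR.** Treat it the same way, with first-pass sigmoid polyp status.

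The cost is a few lines of text, one extra data field with matching specimen labels, somewhat more analysis work, and a result less simple to present than a 2×2 table. No extra patients or procedures are needed.
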